7.4.1 Safety follow-up

For eligible patients, SAE and AE collection and monitoring will continue until 28 days after the last administration of BT1718 or until the patient starts another anti-cancer therapy (see Section 9.3, Safety Reporting). Any drug-related AEs still ongoing after this period will be followed up monthly until resolution to baseline or stabilisation, unless the patient starts another anti-cancer treatment.

Should an Investigator become aware of any BT1718-related AEs or SAEs after this period, these must also be reported to the Sponsor within the expedited timelines in Section 9.4.

7.4.2 Efficacy and survival follow-up

Following pre screening informed consent, all patients should be followed up for survival until the end of the trial, where feasible, whether they subsequently start on trial treatment or not (Section 12). For those no longer on treatment, no further trial visits are required but the site trial team should check the status of the patient at least three monthly (through NHS/HSC electronic data records or by phone calls only if appropriate) until the patient starts another systemic anti-cancer therapy or when PD occurs (if not already occurred) and if the patient remains alive. End of trial may only be declared when all patients have either withdrawn from the trial, died, or completed a minimum of 12 months survival follow-up since their first administration of BT1718.

If the patient is lost to follow-up or has not progressed or died at the time of the final database lock for the Clinical Study Report (CSR), then the information will be censored as not known to have progressed/died at that time.

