- (f) In the event of a Grade 4 neutropenia or Grade 4 thrombocytopenia a full blood count must be performed at least on Day 7 (neutropenia) and Day 5 (thrombocytopenia) after the onset of the event to determine if a dose limiting toxicity has occurred. Continue close monitoring until resolution to Grade 3 or less.
- (g) To be repeated before biopsy procedure if done.
- (h) To be done Cycle 1 and 2, within 1 hour before and 1 hour (+15 mins) after BT1718 administration, then clinically indicated thereafter.
- (i) ECGs should be performed **before** BT1718 administration, and within **1** ½ hours (+15mins) after BT1718 administration during Cycle 1 Day 1. On Cycle 2 Day 1 an ECG should be performed **before** or within 1 ½ hours (+15 mins) after BT1718 administration. From Cycle 2 onwards ECGs should be repeated on Day 1 every two cycles.

- (k) Pharmacokinetic (PK) second sample collection refer to the Laboratory Manual for specific timings.
- (I) Unless performed within previous 28 days or PD seen on previous study scan.
- (m) Monthly **follow-up** required ONLY for those AEs and SAEs considered drug-related (highly probable, probable or possible) and present at off-study visit. Monthly follow-up to continue until resolution, return to baseline, stabilisation or patient starts another anti-cancer treatment.
- (n) All patients should be followed up for first progression and for survival until the end of trial. For those no longer on treatment, the site trial team should check the status of the patient at least three monthly (through NHS/HSC electronic data records or by phone calls only if appropriate) to determine when PD occurs (if not already occurred) and if the patient remains alive.

- (P) The timing of CT/MRI schedule may change in the expansion phase (Phase IIa) depending on tumour type. Any CR or PR needs to be confirmed by a subsequent assessment at least four weeks later.
- (q) Assessments may continue until disease progression or for up two years and can be performed more frequently than every two cycles, if clinical concern or suspicion of disease progression.
- (r) Temperature, blood pressure (seated or lying after 5mins rest) and pulse should be performed before and then repeated 1 hr (+/- 15 mins) after BT1718 administration.

NB: Phase I, Stage 1 is complete.

Observation/ Investigation	Pre screening	Pre treatme evaluations period)	ent s (screening	Cycle 1 (Cycle 2 onwards	Off study	Follow-up	Survival Follow-up

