- (e) **Clinical laboratory assessments** should be performed within the previous seven days of Cycle 1 Day 1 and prior to each planned BT1718 administration on Days 1, 8 and 15 (and Day 22 in Cycle 1 only). After six cycles, the frequency of haematology and biochemistry assessments may decrease at the discretion of the PI and Sponsor but, at a minimum, must be performed on Day 1 of each cycle. Laboratory tests may be performed up to 24 hours prior to BT1718 administration but results must be available and reviewed by the Investigator before BT1718 is given. On Day 1 of each cycle a full biochemistry assessment should be performed and on subsequent dosing days core biochemistry assessment should be performed.
- (f) In the event of a Grade 4 neutropenia or Grade 4 thrombocytopenia a full blood count must be performed at least on Day 7 (neutropenia) and Day 5 (thrombocytopenia) after the onset of the event to determine if a dose limiting toxicity has occurred. Continue close monitoring until resolution to Grade 3 or less.
- (g) To be repeated before biopsy procedure if done.
- (h) To be done Cycle 1 and 2, within 1 hour before and 1 hour (+15 mins) after BT1718 administration then clinically indicated thereafter.

	ithin 1 ½ hours (+15 mins) after BT1718 administration. From Cycle 2 onwards ECGs should be repeated on Day 1 every two cycle
Pharmacokinetic (PK)	sample collection - refer to the Laboratory Manual for specific timings.
Unless performed within previous	28 days or PD seen on previous study scan.
Monthly follow-up required ONLY to continue until resolution, return	' for those AEs and SAEs considered drug-related (highly probable, probable or possible) and present at off-study visit. Monthly follo to baseline, stabilisation or patient starts another anti-cancer treatment.
All patients should be followed up treatment, the site trial team shoul determine when PD occurs (if not died, or completed a minimum of	for first progression and for survival until the end of trial (including patients who do not enter the main trial). For those no longer on Id check the status of the patient at least three monthly (through NHS/HSC electronic data records or by phone calls only if appropria already occurred) and if the patient remains alive. End of trial may only be declared when all patients have either withdrawn from the 12 months survival follow-up since their first administration of BT1718.

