12 DEFINING THE END OF TRIAL

The 'end of trial' is defined as the date when the last patient has completed the 'off-study' visit or the final follow-up (whichever is the latter). The 'off-study' visit is scheduled to take place 28 +/-7 days after the last dose of BT1718 administration. End of trial may only be declared when all patients have either withdrawn from the trial, died, or completed a minimum of 12 months survival follow-up since their first administration of BT1718.

IMP will be available for two years from the latest date that any remaining patients started treatment. After this, any remaining patients will come off-study and the trial will end as above.

The end of trial cannot be declared while any patient is still having study visits or while study data are still being collected, e.g. progression-free or OS data.

If an arrangement becomes possible where patients can continue on prolonged or extended use of IMP, beyond the end of trial, that arrangement will be distinct from the trial and will not prevent the end of trial being declared.

It is the responsibility of the CDD to inform the MHRA and the REC within 90 days of the 'end of the trial' that the trial has closed.

In cases of early termination of the trial (for example, due to toxicity) or a temporary halt by the CDD, the CDD will notify the MHRA and the REC within 15 days of the decision and a detailed, written explanation for the termination/halt will be given.

Recruitment will cease when:

- The drug is considered too toxic to continue treatment before the required number of patients have been recruited.
- The stated number of patients to be recruited has been reached.
- The stated objectives of the trial are achieved.
- The stated objectives of the trial are likely to be met but the trial is stopped due to lack of efficacy (the trial will be closed to recruitment on the date of this decision).

Regardless of the reason for termination, all data available for patients at the time of discontinuation of follow-up must be recorded in the eCRF. All reasons for discontinuation of treatment must be documented.

In terminating the trial, the Sponsor and the Investigators must ensure that adequate consideration is given to the protection of the patient's interest.

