13.5 Pharmacodynamics

13.6 Anti-tumour activity

Documenting anti-tumour activity is a secondary objective of this trial. Patients must receive \geq 66% of the planned dose exposure of BT1718 within Cycle 1 and 2, or at least one full cycle and have a baseline assessment of disease and at least one repeat assessment to be evaluable for response. Patients in the expansion phase must meet the MT1-MMP positivity rate to be evaluable for this objective. Objective responses, the best tumour response achieved by each patient while on trial and the time to progression will be presented in the data listings by cohort.

The response rate (proportion of evaluable patients with objective response) will be reported by cohort. Progression free survival will be calculated from trial entry until the time of documented disease progression or death (whichever occurs first). Patients who are alive and progression free or lost to follow up at the time of analysis will be censored at the time the patient was last known to be alive and progression free. Overall survival will be calculated from trial entry until the time of death from any cause. Patients who are alive or lost to follow up at the time of analysis will be calculated from trial entry until the time of death from any cause. Patients who are alive or lost to follow up at the time of analysis will be censored at the time the patient was last known to be alive. Duration of response will be measured from the date of the first scan where response was seen until date of first RECIST V1.1 progression or death. Median PFS, OS and duration of response will be presented. The PFS and OS rate at 6 months will also be presented. 95% confidence intervals will be reported.

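### Section 7.4.2, read literally, stops the three-monthly status checks at progression or new therapy, against its own survival follow-up rule and footnote (n), and leaves the censoring date open to two readings

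*Protocol*

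**What the plan says.** **Length of follow-up.** Section 7.4.2 opens by requiring that "all patients should be followed up for survival until the end of the trial, where feasible", whether or not they go on to trial treatment. It also says that the end of trial can be declared only when each patient has withdrawn, died or "completed a minimum of 12 months survival follow-up since their first administration of BT1718". Section 12 states the same condition.

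**Status checks.** For patients off treatment, 7.4.2 requires no more visits. The site instead checks status at least every three months, by electronic records or telephone, "until the patient starts another systemic anti-cancer therapy or when PD occurs (if not already occurred) and if the patient remains alive".

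**Schedules of events.** Footnote (n) to the Stage 1 table (7.5.1) says: "All patients should be followed up for first progression and for survival until the end of trial". It gives the purpose of the checks as "to determine when PD occurs (if not already occurred) and if the patient remains alive". The footnote to the table for Stage 2 and Phase IIa (7.5.2) likewise sets follow-up "for first progression and for survival until the end of trial (including patients who do not enter the main trial"). Neither footnote ends the checks at progression or at new therapy.

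**Censoring.** For patients who are lost, or have no event at the final database lock, 7.4.2 says "then the information will be censored as not known to have progressed/died at that time". Section 13.6 says that PFS "will be censored at the time the patient was last known to be alive and progression free" and that OS is censored at the date last known alive. It gives no censoring rule for new therapy.

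**Endpoints.** Section 3.1.2 lists PFS, the six-month PFS rate and, where available, OS as secondary endpoints. Section 13.6 reports medians and six-month rates with 95% confidence intervals.

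**The concern.** After treatment ends, the three-monthly check is the only scheduled source of follow-up data. Section 5.6 makes progression a reason to stop treatment, so many patients will already meet the literal stop condition on the day they leave treatment and would get no checks at all. A site working from 7.4.2 and a site working from footnote (n) would then collect different data.

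The missing information would not be missing at random. It would be missing because the patient had progressed or had been moved to another therapy, and both are related to prognosis. The loose censoring sentence adds a second route to distortion: if a lost patient is dated at database lock, the curve is credited with event-free time that nobody observed.

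**Working it through.** **1. The texts side by side**

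| Question | 7.4.2 | Footnote (n), both tables | 13.6 |
|---|---|---|---|
| How long is survival followed? | To end of trial, where feasible | To end of trial | Not stated |
| When do the checks stop? | At new systemic therapy or progression, read literally | No stop at either | Not stated |
| Is PFS censored at new therapy? | Not stated, but checks stop there | No | No |
| Censoring date | Unclear: status at lock, or date of lock | Not stated | Last known alive (OS); last known alive and progression free (PFS) |

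The conflict lies between the second and first rows of 7.4.2, and between 7.4.2 and footnote (n).

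**2. What each stop can do**

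- *Stop at progression, PFS:* no effect, because the event has already happened.
- *Stop at progression, OS:* if later deaths are missed and patients are censored at progression, OS is too high. If deaths are still found but survivors' alive dates are no longer updated, OS is too low.
- *Stop at new therapy, PFS:* later progressions are missed. If therapy was changed because progression was near, PFS is too high.

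**3. Size under assumptions**

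The protocol gives no expected PFS or OS, event count or loss rate, so there is no planned figure to reproduce. The following are assumed: exponential times; median time to progression 2, 3 or 4 months; median survival after progression 5, 6 or 7 months; median time to death without progression 30 months; uniform accrual over 18 months; lock 12 months after last entry. Each scenario was simulated with 400,000 patients.

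Closed-form check of the middle scenario. The monthly hazards are λ = ln 2/3 = 0.2310 (progression), h = ln 2/30 = 0.0231 (death without progression) and μ = ln 2/6 = 0.1155 (death after progression).

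- PFS(6) = exp(−(λ+h)·6) = exp(−1.525) = 0.218. Simulated: 0.217.
- OS(6) = PFS(6) + [λ/(λ+h−μ)]·[exp(−6μ) − PFS(6)] = 0.218 + 1.667 × (0.500 − 0.218) = 0.688. Simulated: 0.688.

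Median OS in months, by share of progressed patients affected:

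| Scenario (progression / post-progression) | Full follow-up | Censored at progression: 25% | 50% | Deaths found, alive dates stop: 25% | 50% | 100% |
|---|---|---|---|---|---|---|
| 2 / 5 | 7.5 | 7.9 | 8.5 | 7.4 | 7.2 | 7.0 |
| 3 / 6 | 9.4 | 10.0 | 10.8 | 9.2 | 9.0 | 8.5 |
| 4 / 7 | 11.3 | 11.9 | 12.9 | 10.9 | 10.6 | 9.9 |

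If every progressed patient were censored at progression, only deaths without progression would remain. Six-month OS would then be estimated as 2^(−6/30) = 0.871 (simulated 0.870) in place of 0.688. That is the limiting case, not the expected one.

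Dating losses at lock instead of last contact (middle scenario, nominal random loss of 5%, 10% and 20%, with loss times uniform over 12 months):

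- median OS goes from 9.4 to 9.6, 9.9 and 10.4 months;
- six-month PFS goes from 21.7% to 22.5%, 23.2% and 24.7%.

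With the 13.6 dates, the same random loss leaves both essentially unchanged.

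Censoring PFS at a new therapy started at 80% of the time to the PFS event, in 10% or 20% of patients, moves the middle-scenario median from 2.7 to 3.0 or 3.3 months.

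**4. Against sampling error**

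For 16 patients and a six-month OS of 0.688, the approximate 95% half-width is 1.96 × √(0.688 × 0.312/16) = 0.227. With 25% or 50% of progressed patients censored at progression, the estimate becomes 0.711 or 0.742, a shift of 2.3 or 5.4 percentage points. That is well inside the noise of one cohort, although it is systematic.

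**The case against.** The strongest reply is that 7.4.2 plainly intends survival follow-up to continue. Its first sentence says so and it carries the 12-month condition. The stop clause is ungrammatical and looks like a damaged copy of the footnote (n) sentence, and the table for the phase still running has the clear version. This stands as evidence of intent. It does not cure the clause, because the reference to new systemic therapy appears nowhere in footnote (n) and gives a site an instruction it could follow.

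Four stronger readings are tempting, and the documents do not support them.

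- *That 7.4.2 contradicts Section 12.* Both carry the same 12-month condition. Without checks a site would struggle to show that condition met for a patient still alive, but that is a practical consequence, not a conflict of text.
- *That 7.4.2 censors losses at database lock.* The closing words of its sentence may equally describe the status known at lock, with 13.6 supplying the date. The fault is that two readings are possible.
- *That OS and PFS are biased upward.* Stopping at progression cannot move PFS, and the direction for OS depends on whether deaths or only alive dates are lost.
- *That PFS and OS should start at first dose instead of trial entry.* The 12-month minimum is an end-of-trial condition, not an endpoint origin, and nothing in this point argues for the change.

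It is also fair that the stakes are limited. OS is reported only where available, the presentation is descriptive, and the benchmarks in Section 13.1 use response rate.

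**Conclusion.** The point holds as an internal inconsistency in follow-up together with an ambiguous censoring date. The literal stop clause in 7.4.2 disagrees with the same section's survival follow-up and with footnote (n) in both tables. Stopping observation at new therapy also does not fit the PFS definition in 13.6. If applied, it can distort OS in either direction, and it can distort PFS through the new-therapy stop or the lock-date reading.

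In the middle assumed scenario, median OS of 9.4 months becomes 10.0 to 10.8 when 25% to 50% of progressed patients are censored at progression, or 9.2 to 9.0 when only alive dates are lost. None of these rates comes from the protocol, and how many sites would apply the clause literally is unknown. The endpoints are secondary and descriptive in cohorts of about 16. The clause should be corrected, but no stated decision rule depends on it.

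**What to change.** In 7.4.2, replace the stop clause with the purpose given in footnote (n). State that vital status, and progression if not yet documented, is checked at least every three months until death, withdrawal or end of trial, regardless of progression or new systemic therapy. Replace the 7.4.2 censoring sentence with a reference to the dates in 13.6: last known alive for OS, last known alive and progression free for PFS.

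The cost is an amendment of wording. No visits are added, because the checks use electronic records or telephone and footnote (n) already plans follow-up to the end of the trial.

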7.5 Schedule of events

7.5.1 Phase I, stage 1

Observation/ Investigation	Pre screening (Expansion Phase only)	Pre treatm evaluation (screening	nent Is g period)		Cycle 1						Cycle 2 onwards	Off study	Follow-up	Survival Follow-up
	6 months to Day-7	Within 28 days (Day -28 to Pre dose Day 1)	Within 8 days before study inclusion	Day 1	Day 4	Day 8	Day 11	Day 15	Day 18	Day 22	Days 1, 4, 8, 11, 15 and 18	Off study: (28 ±7 days after last dose of IMP)	At least monthly	Until end of trial
Written informed consent	Х	Х												
Archival or fresh tumour biopsy for MT1-MMP ICH profiling (a)	x													
Demographics		х												
Medical history		Х												
Adverse event evaluation		From informed	date of I consent				(Continual	lly review	,		X	Until resolution (m)	
Concomitant treatments		From informed	date of I consent				(Continual	lly review			Х		
Radiological disease assessment		X			At the end of every two cycles (p) (q)					es (p) (q))	X (I)		
Clinical disease assessment (if applicable)			X		At the end of every two cycles (q)					rcles (q)		X		
Pregnancy test (b)			X									X		

Observation/ Investigation	Pre screening (Expansion Phase only)	Pre treatm evaluation (screening	ient is g period)		Cycle 1 Cycle 2 onwards						Off study	Follow-up	Survival Follow-up	
	6 months to Day-7	Within 28 days (Day -28 to Pre dose Day 1)	Within 8 days before study inclusion	Day 1	Day 4	Day 8	Day 11	Day 15	Day 18	Day 22	Days 1, 4, 8, 11, 15 and 18	Off study: (28 ±7 days after last dose of IMP)	At least monthly	Until end of trial
Physical examination (c)			Х		Symptom-directed, repeat as clinically indicated						Symptom- directed (if clinically indicated)			
Height			Х											
Weight (d)			Х	Х							X (Day 1 only)			
Body surface area (BSA)			X	Х							X (Day 1 only)			
Bloods for haematology and biochemistry (e) (f)			X	Х	Х	Х	х	X	X	X	X (Day 1, 8 and 15 only)	Х		
Coagulation tests (g)			X											
Renal function			Х											
Urinalysis			Х	Х						Х	X (Day 1 only)	Х		
Glucose finger-prick test before and after BT1718 administration (diabetic patients only) (h)				Х	X	Х	Х	X	X		X			
Electrocardiogram (ECG) (i)			X	Х							X (Day 1 only)	Х		
BT1718 administration (+/- 1 day)				Х	X	Х	Х	X	X		X			

Observation/ Investigation	Pre screening (Expansion Phase only)	Pre treatm evaluation (screening	ient is g period)	Cycle 1							Cycle 2 onwards	Off study	Follow-up	Survival Follow-up
	6 months to Day-7	Within 28 days (Day -28 to Pre dose Day 1)	Within 8 days before study inclusion	Day 1	Day 4	Day 8	Day 11	Day 15	Day 18	Day 22	Days 1, 4, 8, 11, 15 and 18	Off study: (28 ±7 days after last dose of IMP)	At least monthly	Until end of trial
Temperature, blood pressure (seated or lying after 5mins rest) and pulse (r)			X	x	X	X	X	X	X	X	X	X		
WHO performance status			Х	Х	Х	Х	Х	Х	Х	Х	Х	Х		
		•												
Blood for PK (k)				Refer	to Lab	manua	l for ex	act timin	gs					
Follow-up contact for survival/ progression (n)														X

(a) Archival sample if available in Phase I, the dose escalation phase (retrospective MT1-MMP status). Tumour sample, whether archival or fresh, is **mandatory** in Phase IIa, the expansion phase to confirm patient eligibility. Archival tumour biopsy sample can be obtained within six months prior to the first dose. Fresh screening tumour biopsy must be performed/obtained within eight weeks prior to first dose.

(b) **Pregnancy test**: For female patients of child bearing potential.

(c) Complete **physical examination** to be performed Pre treatment then all subsequent examinations can be symptom-directed and only performed as clinically indicated

(d) Screening **weight** can be used to calculate BSA for Cycle 1.

CRUKD/17/009 Protocol Final 10.0 14Oct2022 EudraCT number: 2016-004633-24 ©Cancer Research UK Page 61 of 99

- (e) **Clinical laboratory assessments** should be performed within the previous seven days of Cycle 1 Day 1 and prior to each planned BT1718 administration on Days 1, 4, 8, 11, 15, 18 and 22 of Cycle 1. From Cycle 2 onwards, laboratory assessments must be performed and checked prior to BT1718 administration on Days 1, 8 and 15 and thereafter if clinically indicated. After six cycles, the frequency of haematology and biochemistry assessments may decrease at the discretion of the PI and Sponsor but, at a minimum, must be performed on Day 1 of each cycle. Laboratory tests may be performed up to 24 hours prior to BT1718 administration but results must be available and reviewed by the Investigator before BT1718 is given. On Day 1 of each cycle a full biochemistry assessment should be performed and on subsequent dosing days core biochemistry assessment should be performed.
- (f) In the event of a Grade 4 neutropenia or Grade 4 thrombocytopenia a full blood count must be performed at least on Day 7 (neutropenia) and Day 5 (thrombocytopenia) after the onset of the event to determine if a dose limiting toxicity has occurred. Continue close monitoring until resolution to Grade 3 or less.
- (g) To be repeated before biopsy procedure if done.
- (h) To be done Cycle 1 and 2, within 1 hour before and 1 hour (+15 mins) after BT1718 administration, then clinically indicated thereafter.
- (i) ECGs should be performed **before** BT1718 administration, and within **1** ½ hours (+15mins) after BT1718 administration during Cycle 1 Day 1. On Cycle 2 Day 1 an ECG should be performed **before** or within 1 ½ hours (+15 mins) after BT1718 administration. From Cycle 2 onwards ECGs should be repeated on Day 1 every two cycles.

- (k) Pharmacokinetic (PK) second sample collection refer to the Laboratory Manual for specific timings.
- (I) Unless performed within previous 28 days or PD seen on previous study scan.
- (m) Monthly **follow-up** required ONLY for those AEs and SAEs considered drug-related (highly probable, probable or possible) and present at off-study visit. Monthly follow-up to continue until resolution, return to baseline, stabilisation or patient starts another anti-cancer treatment.
- (n) All patients should be followed up for first progression and for survival until the end of trial. For those no longer on treatment, the site trial team should check the status of the patient at least three monthly (through NHS/HSC electronic data records or by phone calls only if appropriate) to determine when PD occurs (if not already occurred) and if the patient remains alive.

- (P) The timing of CT/MRI schedule may change in the expansion phase (Phase IIa) depending on tumour type. Any CR or PR needs to be confirmed by a subsequent assessment at least four weeks later.
- (q) Assessments may continue until disease progression or for up two years and can be performed more frequently than every two cycles, if clinical concern or suspicion of disease progression.
- (r) Temperature, blood pressure (seated or lying after 5mins rest) and pulse should be performed before and then repeated 1 hr (+/- 15 mins) after BT1718 administration.

NB: Phase I, Stage 1 is complete.

Observation/ Investigation	Pre screening	Pre treatme evaluations period)	ent s (screening	Cycle 1 (Cycle 2 onwards	Off study	Follow-up	Survival Follow-up
	6 months to Day-7 (Expansion phase only)	Within 28 days (Day -28 to Pre dose Day 1)	Within 8 days before study inclusion	Day 1	Day 8	Day 15	Day 22	Days 1, 8 and 15	Off study: (28 ±7 days after last dose of IMP)	At least monthly	Until end of trial
Written informed consent	х	Х									
Archival or fresh tumour biopsy for MT1-MMP IHC profiling (a)	X										
Demographics		Х									
Medical history		X									
Adverse event evaluation		From date col	e of informed nsent	Continually review			V	Х	Until resolution (m)		
Concomitant treatments		From date co	e of informed nsent			Continua	lly reviev	v	х		
Radiological disease assessment		X		Day	15 – Da	y 28 of e	very two	cycles (p) (q)	X (I)		
Clinical disease assessment (if applicable)			X	Day	y 15 – C	ay 28 of	every tw	o cycles (q)	X		
Pregnancy test (b)			X						X		
Physical examination (c)			X	Sy	/mptom·	-directed, indic	repeat a ated	as clinically	Symptom- directed (if clinically indicated)		
Height			Х								
Weight (d)			X	Х				X (Day 1 only)			
Body surface area (BSA)			X	Х				X (Day 1 onlv)			

